8.1.6 Early Treatment Termination

If the subject prematurely discontinues study drug treatment or is withdrawn from the study, an Early Treatment Termination (ETT) Visit should be scheduled as soon as possible after the last dose of study drug. Such subjects will also be required to complete the Safety Follow-up Visit, approximately 28 days \pm 7 days after their last dose of study drug. The assessments performed at the Safety Follow-up Visit are listed in [Table 3-2](#).

If the ETT Visit occurs 3 weeks or later following the last dose of study drug, then the ETT Visit will replace the Safety Follow-up Visit, and a separate Safety Follow-up Visit will not be required.

Subjects who prematurely discontinue study drug treatment will continue to complete all other scheduled study visits for assessments of efficacy (spirometry, sweat chloride, and CFQ-R) and [REDACTED]

[REDACTED] through the end of the Treatment Period in which discontinuation occurred, as detailed in the Schedule of Assessments ([Section 3](#)).

If the subject withdraws from the study and also withdraws consent for disclosure of future information, no further evaluations will be performed, and no additional data will be

collected. Vertex may retain and continue to use any data collected before such withdrawal of consent.

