  - For all efficacy parameters, if there are multiple measurements within a visit window, the record at the scheduled visit will be used. If there are no measurements at the scheduled visit:
    - the record closest to the target day will be used.
    - If there are multiple records with the same distance to the target day, the latest record will be used.
    - Assessments at early treatment termination (ETT) visit will follow the windowing rules for regular visits up to Week 24.

- A safety follow-up visit (SFUV) assessment will follow the windowing rules for regular visits if it falls within the upper boundary of the visit window for Week 8 (period 1) or Week 24 (period 2), or remain as SFUV otherwise.
- For all safety parameters, if there are multiple measurements within a visit window, then 1) the record closest to the target day will be used; 2) if there are multiple records within the same distance from the target day, the latest record will be used; 3) SFUV will not be windowed, instead, used per nominal visit in relevant analyses.

Note: spirometry assessments, BMI, weight, and height will be used for both efficacy and safety purposes. The corresponding measurements will follow visit windowing rules for efficacy.

**Incomplete/Missing data** will not be imputed, unless otherwise specified.

**Outliers:** No formal statistical analyses will be performed to detect or remedy the presence of statistical outliers, unless otherwise specified.

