#### **8.4.2 Clinical Laboratory Values**

For treatment-emergent laboratory measurements, the raw values and change from period baseline values for the continuous hematology, chemistry and coagulation results will be summarized in SI units by treatment group at each scheduled time point. For hematology, coagulation and chemistry measurements, the number and percentage of subjects with an abnormal low (<LLN) value and an abnormal high (>ULN) value at each analysis visit will be summarized.

The number and percentage of subjects with hematology, chemistry and coagulation values meeting the defined threshold criteria during the visit window for analysis visits will be summarized by analysis visit. Similarly, the hematology, chemistry and coagulation values meeting the defined threshold criteria during the overall TE period will be presented. The threshold analysis criteria are provided in Section 10.5 (Table 10-7 and Table 10-8).

For all LFT results (alanine aminotransferase [ALT], aspartate aminotransferase [AST], alkaline phosphatase [ALP], direct bilirubin, total bilirubin, and gamma-glutamyl transferase [GGT]), the following additional analyses will be conducted:

- A listing of subjects with elevated LFT results during the TE period will be presented. For each subject in the listing, LFT assessments at all visits during the TE period with elevated LFT will be included.
- For each of the LFTs, mean values ( $\pm$ SD) will be plotted by visit.
- The incidence of LFTs meeting threshold analysis criteria during the TE period against the period baseline threshold criteria will be summarized by treatment group (only worsening of the shift from period baseline will be presented).
- A scatter plot of the maximum ALT value across visits versus the maximum total bilirubin value also will be presented. The ALT and Total bilirubin values will be presented on a logarithmic scale. The graph will be divided into 4 quadrants with a vertical line corresponding to 3xULN for ALT and a horizontal line corresponding to 2xULN for total bilirubin. A similar graph of maximum AST value versus maximum total bilirubin value will be presented as well.

A summary table for the shift from period baseline to the value at Week 8 will be presented by treatment group for vitamin levels and lipid panel. A box plot of vitamin levels and lipid panel will also be plotted against visit.

For amylase and lipase, mean values ( $\pm$ SD) will be plotted by visit.

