## 8.5 Safety Supportive Endpoints

### 8.5.1 Predose Spirometry

As supportive safety data, the following summaries regarding the decline in predose spirometry will be provided:

- Number and percentage of subjects with  $\geq 10$ ,  $\geq 15$  or  $\geq 20$  percentage points decrease in absolute change from period baseline in ppFEV1 at each post-baseline visit.
- Number and percentage of subjects with  $\geq 0.2$  L decrease in absolute change from period baseline in FEV1 at each post-baseline visit.

Subjects with  $\geq 10$  percentage points decrease in absolute change from period baseline in ppFEV1 or  $\geq 0.2$  L decrease in the absolute change from period baseline in FEV1 will be listed. The listing will include raw values and absolute/relative changes from period baseline in ppFEV1 and FEV1 at each visit from the period in which the decline criteria was met.

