z All concomitant medications are collected through the Safety Follow-up Visit for all subjects. For subjects who prematurely discontinue study drug treatment and are followed for certain efficacy assessments after the ETT Visit (see Section 8.1.6 of Clinical Study Protocol), concomitant antibiotic therapy for ‘sinopulmonary signs/symptoms’ are collected through the Week 24 Visit, as described in Section 11.6.4.5.1 of Clinical Study Protocol.

 
• Labs                             
 
○ Coagulation
 
○ Urinalysis
 
 
 
	1-Baseline	Baseline	1	[screening visit, pre-dose Day 1]
	1 - Week 8	Week 8	57	[1*, 71]
	1 - Week 12 (Safety Evaluation Visit)	Safety Follow-up Visit	NA	Use the nominal visit name
	2-Baseline	Baseline	1	[end of TE period for first period +1 , pre-dose Week 17]
	2 - Week 24	Week 8	57	[1*, 71]
	ETT		NA	Follow the individual visit window to be mapped to individual visits
	2 - Safety Follow-up Visit	Safety Follow-up Visit	NA	Use the nominal visit name

 
• Labs                             
 
○ Vitamin levels
 
○ Lipid panel
 
 
 
	1-Baseline	Baseline	1	[screening visit, pre-dose Day 1]
	1 - Week 8	Week 8	57	[1*, 71]
	2-Baseline	Baseline	1	[end of TE period for first period +1 , pre-dose Week 17]
	2 - Week 24	Week 8	57	[1*, 71]
	ETT		NA	Follow the individual visit window to be mapped to individual visits

 
• Spirometry
 
• Standard 12-lead ECG
 
	1-Baseline	Baseline	1	[screening visit, pre-dose Day 1]
	1 – Day 1 Predose and Postdose	Day 1	1	Nominal
	1 – Day 15 Predose and Postdose	Day 15	15	Nominal
		Day 15	15	[1*, 15] if no nominal Day 15
	1 – Week 4	Week 4	29	[Nominal Day 15+1, 43] if there is nominal Day 15; [16, 43] otherwise.
	1 – Week 8	Week 8	57	[44, 71]
	1 - Week 12 (Safety Evaluation Visit)	Safety Follow-up Visit	NA	Use the nominal visit name †
	2 - Baseline	Baseline	1	[end of TE period for first period +1 , pre-dose Week 17]
	2 – Week 17 Predose and Postdose	Day 1	1	Nominal
	2 – Week 18 Predose and Postdose	Day 15	15	Nominal
		Day 15	15	[1*, 15] if no nominal Week 18
	2 – Week 20	Week 4	29	[Nominal Week 18+1, 43] if there is nominal Week 18; [16, 43] otherwise.
	2 – Week 24	Week 8	57	[44, 71]
	ETT		NA	Follow the individual visit window to be mapped to individual visits

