## Note:

1. For spirometry and ECG data on Day 1 and Day 15 of each treatment period, no visit windowing rule shall be applied. Instead, nominal visit will be used.
2. On Day 1 of period 1, the pre-dose ECG measurements are collected as triplicates. The average of pre-dose triplicates will be used as baseline. Only the pre-dose assessments of the triplicate will be used for the baseline. If all the measurements for triplicates are missing or post-dose, the last non-missing pre-dose assessment will be used as the baseline.
3. For all efficacy parameters, if there are multiple measurements within a visit window, the record at the scheduled visit will be used.
  - If there are no measurements at the scheduled visit, then the record closest to the target day will be used
  - If there are multiple records with the same distance to the target day, the latest record will be used.
  - Assessments at early treatment termination (ETT) visit will follow the windowing rules for regular visits up to Week 24.
  - A safety follow-up visit (SFUV) assessment will follow the windowing rules for regular visits if it falls within the upper boundary of the visit window for Week 8 (period 1) or Week 24 (period 2), or remain as SFUV otherwise.
4. For all safety parameters:
  - If there are multiple measurements within a visit window, then the record closest to the target day will be used
  - If there are multiple records with the same distance to the target day, the latest record will be used.
5. Spirometry, BMI, Weight and Height will follow the efficacy windowing rules.

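### The predose FEV1-decline tables count by visit only, so a fall seen only at an ETT or unscheduled visit goes uncounted when the scheduled visits are attended

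*SAP*

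**What the plan says.** - **Decline tables.** SAP 8.5.1 gives the number and percentage of subjects with a "percentage points decrease in absolute change from period baseline in ppFEV 1 at each post-baseline visit", at cut-offs of 10, 15 and 20 points, and a parallel count for a fall of at least 0.2 L in FEV1. It adds a listing of subjects who fall by at least 10 points or 0.2 L.
- **Windowing.** SAP 8.1 notes that spirometry serves both efficacy and safety, and adds: "The corresponding measurements will follow visit windowing rules for efficacy". Note 5 in SAP 10.2 repeats it: "Spirometry, BMI, Weight and Height will follow the efficacy windowing rules". Under the efficacy rule, "if there are multiple measurements within a visit window, the record at the scheduled visit will be used". Closeness to the target day matters only when the window holds no scheduled record.
- **ETT records.** "Assessments at early treatment termination (ETT) visit will follow the windowing rules for regular visits up to Week 24". The ETT row of the spirometry windows in SAP 10.2 agrees: "Follow the individual visit window to be mapped to individual visits". ETT spirometry therefore has no row of its own.
- **Attendance after stopping drug.** Protocol Table 3-2 takes spirometry at the ETT Visit. Under protocol 8.1.6, subjects who stop early "will continue to complete all other scheduled study visits for assessments of efficacy (spirometry, sweat chloride, and CFQ-R"), to the end of that Treatment Period.
- **Other safety measures.** For laboratory tests (SAP 8.4.2), "values meeting the defined threshold criteria during the overall TE period will be presented". ECGs (8.4.3) and vital signs (8.4.4) have the same whole-period count, and pulse oximetry (8.4.5) uses the lowest TE value.

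**The concern.** A subject who stops drug because lung function has dropped is likely to have that drop measured at the ETT Visit or an unscheduled visit. Those are the records that give way when a scheduled record exists, and the protocol asks the subject to go on supplying scheduled records. The decline tables can then show no fall for someone whose data contain one.

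An any-time count would recover these values, and the SAP has one for its other threshold-based safety measures. SAP 8.1 even provides for unscheduled values to enter minimum on-treatment values and minimum changes in safety analyses, but 8.5.1 derives no minimum. By-visit rows also cannot be added up to the number of subjects who ever declined. At stake is whether the report can state, by treatment, how many subjects had a fall of a given size.

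**Working it through.** The plan gives no figure to reproduce here. The check applies the written rules to every possible ETT day.

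**Inputs (SAP 10.2, spirometry; days counted within a period).** Day 15 uses the nominal visit, with a fallback window of Days 1 to 15 if there is none. Week 4 has target Day 29 and runs from the day after nominal Day 15 (otherwise Day 16) to Day 43. Week 8 has target Day 57 and runs from Day 44 to Day 71.

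**One case.** Last dose Day 43, ETT Day 46 with a 15-point fall, Week 8 visit on Day 57 with recovery. Both records lie in Days 44 to 71. The Day 57 record is the scheduled one, so it is used and no decline is counted. The Safety Follow-up Visit is 28 ± 7 days after the last dose, so no earlier than Day 43 + 21 = Day 64. Day 57 is therefore still inside the TE period.

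**All ETT days.** Days 2 to 56 are 55 days. Removing the visit days 15 and 29 leaves 53.

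| ETT day | Days | Scheduled visits attended on target | No scheduled visit after ETT |
|---|---|---|---|
| 2–14 | 13 | in no window, since nominal Day 15 exists | ETT used (fallback window) |
| 16–28 | 13 | displaced by later Week 4 record | ETT used |
| 30–43 | 14 | displaced by earlier Week 4 record | displaced by earlier Week 4 record |
| 44–56 | 13 | displaced by later Week 8 record | ETT used |

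With visits attended, the ETT value enters the tables on 0 of 53 days. A later scheduled record, off drug for a subject who has stopped, displaces it on 13 + 13 = 26 days. The earlier Week 4 record displaces it on 14, and on 13 it has no window. With no later visit, it is used on 13 + 13 + 13 = 39 days and displaced on 14.

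**Would the safety windowing rule help?** That rule also keeps one record per window, the one closest to target. With visits on target it again keeps 0 of 53, and in the case above it also picks Day 57. With the scheduled visit moved by up to 5 days either way, each window has 11 × 27 = 297 combinations of visit day and other day; the safety rule keeps the other record in 55 of them (55/297 = 18.5%).

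**Does the end of the TE period remove the later off-drug value?** Generally not. The longest gap within one window from ETT to a later scheduled visit is 34 − 16 = 18 days (Week 4) or 62 − 44 = 18 days (Week 8). The earliest Safety Follow-up Visit is 21 days after the last dose. The exception is an ETT Visit held some days after the last dose.

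**The case against.** **The windowing rule looks like the cause, so a reader might infer that exempting spirometry from it is the cure.** It is not. The safety rule also keeps one record per window and would drop most ETT values. The cause is a by-visit count with no any-time count beside it.

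**A reader might infer that an off-drug recovery value always replaces the ETT value.** That holds on 26 of 53 days. On 14 the displacing record is the earlier Week 4 value, and if the window has no scheduled record the ETT value is used.

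**The signal may not be lost.** SAP 8.5.1 lists subjects who decline, and SAP 8.1 lets unscheduled values into listings where appropriate. A subject who stops for worsening should also appear under reasons for discontinuation and, if an adverse event is recorded, among events leading to discontinuation. This stands in part. The SAP does not say whether the listing criterion uses windowed or all records, and neither a listing nor an event table gives the rate of a measured fall by treatment.

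**A reader might infer a bias in favour of active drug.** No figure in the documents supports that. The rule is the same in every arm, and the direction depends on which arm has more subjects stopping with a reversible fall.

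**A reader might size the problem from dropout** (10% assumed; 4.6% to 7.7% in earlier studies). Those rates count subjects who leave. Displacement by a later value affects subjects who stop drug and keep attending, and the documents give no number for them.

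**Conclusion.** The point holds for the tables in SAP 8.5.1. When the scheduled visits are attended, as the protocol requires, a fall in predose ppFEV1 or FEV1 recorded only at an ETT or unscheduled visit is not counted. On target visit days that is 53 of 53 possible ETT days. The result assumes that the SAP 10.2 windows are applied as written, including the Day 15 fallback.

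Its reach is limited. These are descriptive, supportive safety summaries, and no primary or key secondary analysis changes. The number of subjects affected and the direction of any between-arm effect cannot be taken from the documents. Parts of the SAP, including section 8.6, are redacted, so the absence of an any-time row is established only for the visible text. It is a low-cost improvement worth making before database lock.

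**What to change.** In SAP 8.5.1, alongside the by-visit rows:

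- Add the number and percentage of subjects, by treatment, with a fall from period baseline of at least 10, 15 or 20 points in ppFEV1, or at least 0.2 L in FEV1, at any time in the TE period. Base it on the minimum of all predose records: scheduled, unscheduled and ETT.
- State that the listing is driven from the same records.

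Leave the windowing rules in SAP 8.1 and 10.2 unchanged.

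The cost is SAP wording, one derived variable and one table block, with no new data or visits. The downside is that any-time rates are higher and noisier in every arm. As an illustration only, assume a change SD of 7 points (the planning value for the Week 4 and 8 average, not for a single visit), mean change 0, three visits and between-visit correlation of 0.3 to 0.7. A by-visit row then shows Φ(−10/7) = 7.7% with a fall of at least 10 points, while simulation gives 15% to 19% with such a fall at some visit. The new row should therefore be read against placebo and next to the by-visit rows, not in place of them.

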## 8.2 Background Characteristics

Unless otherwise defined, the FAS will be used for all analyses of background data. The background analyses will be performed according to the treatment to which the subject was assigned in each period.

### 8.2.1 Subject Disposition

The number of subjects in the following categories will be presented by treatment group:

- All Subjects Set (randomized or dosed)
- Randomized
- Full Analysis Set (FAS)
- Safety Set

The number of subjects in the following categories will be presented by treatment group for each period (Period 1 and Period 2):

- Full Analysis Set (FAS)
- Safety Set

The number and percentage (based on Safety Set) of subjects in each of the following disposition categories will be presented by treatment group for each period (Period 1 and Period 2):

- Completed treatment regimen
- Prematurely discontinued the treatment (any tablet) and the reasons for discontinuations
- Prematurely discontinued the study and the reasons for discontinuations

The number and percentage (based on the overall Safety Set) of subjects in each of the following disposition categories will be presented by treatment group:

- Completed treatment regimen in both periods
- Completed study
- Rollover to extension

A listing will be provided for subjects who discontinued treatment or who discontinued study, along with reasons for discontinuations.

The number and percentage of randomized subjects will be summarized by stratification factor, and by country and by site, using the number of subjects being randomized in each treatment sequence as the denominator. A randomization listing also will be provided.

### **8.2.2 Demographics and Baseline Characteristics**

Demographic and study baseline characteristics data will be summarized by treatment group based on the FAS for each period (Period 1 and Period 2).

Demographic data will include the following:

- Age at screening
- Age group at screening (< 18, and ≥18 years)
- Sex
- Ethnicity (Hispanic or Latino, not Hispanic or Latino, and not collected per local regulations)
- Race (White, Black or African American, Asian, American Indian or Alaska Native, Native Hawaiian or Other Pacific Islander, and Other)
- Geographic region (North America and Europe)

Note: Australia and Israel will be presented under Europe.

Baseline characteristics will include the following:

- Weight (kg) at study baseline
- Height (cm) at study baseline
- BMI (kg/m^2) at study baseline

Stratification categories will include the following:

- ppFEV1 at screening (<70, and ≥70)
- Residual function mutation (Class V non-canonical splice, and Classes II to IV residual function)

Disease characteristics will include the following:

- ppFEV1 at study baseline (<40, ≥40 to <70, ≥70 to ≤90 and >90)

- ppFEV1 at study baseline
- Sweat chloride at study baseline
- CFQ-R at study baseline
- FEV1 (L) at study baseline
- FVC (L) at study baseline
- Percent predicted FVC at study baseline
- FEF25-75% (L/sec) at study baseline
- Percent predicted FEF25-75% at study baseline
- FEV1/FVC at study baseline
- Use of dornase alfa
- Use of inhaled antibiotic
- Use of azithromycin
- Use of bronchodilator
- Use of inhaled bronchodilator (short-acting only, [short-acting and long-acting] or long-acting only)
- Use of inhaled hypertonic saline
- Use of inhaled corticosteroids
- Colonization of *Pseudomonas aeruginosa* (Positive, Negative)
- Pancreatic Insufficient (defined as fecal elastase-1 value of <200 µg/g)

In addition, data listings will also be provided for:

- informed consent
- Inclusion/Exclusion criteria violation (for subjects with any such violations)

### 8.2.3 Medical History

Medical history will be coded by using the Medical Dictionary for Regulatory Activities (MedDRA).

For the FAS, medical history will be summarized descriptively by treatment group, system organ class (SOC) and preferred term (PT) for each period (Period 1 and Period 2). The corresponding data listing also will be provided.

In addition, the number of subjects reported to have had positive cultures for respiratory pathogens in 2 years prior to screening (i.e., answered yes on the respiratory microbiology form) will be summarized by test and subcategories within the test for each period. The corresponding data listing will be provided. Hospitalization and clinic visit history in the past year will be listed.

## 8.2.4 Prior and Concomitant Medications

Medications taken during this study will be coded using the World Health Organization Drug Dictionary Enhanced (WHO-DDE) and categorized as follows:

- **Prior medication:** any medication that started before the first dose of study drug in the study, regardless of when it ended.
- **Concomitant medication:** medication continued or newly received during the TE period for Treatment Period 1 or Treatment Period 2. If a subject took a medication during a specific Treatment Period, this medication will be attributed to the treatment the subject received during this Treatment Period. As a result, 1 medication could be attributed to more than 1 study drug for an individual subject.
- **Post-treatment medication:** medication continued or newly received after the TE period for Treatment Period 2, or between the TE periods for Treatment Period 1 and Treatment Period 2, or after the TE period for Treatment Period 1 for subjects who do not have Treatment Period 2.

A given medication can be classified as a prior medication, a concomitant medication, or a post-treatment medication; both prior and concomitant; both concomitant and post-treatment; or prior, concomitant, and post-treatment. If a medication has a missing or partial missing start/end date or time and it cannot be determined whether the medication was taken before initial dosing, concomitantly, or post-treatment, it will be considered as prior, concomitant, and post-treatment.

For the FAS, prior medications and concomitant medications will be summarized descriptively by: 1) treatment group, preferred name (PN); and 2) treatment group, anatomic class (ATC) level 1, ATC level 2, and PN. Prior medication summaries will be by period (Period 1 and Period 2). Post-treatment medications will be listed for each subject.

As an intermediate step for programming purposes, medications with missing or partially missing start dates will use 2000 to impute for the missing year, January for the missing month, and 1 for the missing day. Medications with missing or partially missing stop dates will use 2050 to impute for the missing year, December for the missing month, and the last day of the month for the missing day. The logic to decide the category of a medication is presented in [Table 8-1](#):

